### 5.3.3.2 Bone remodelling

The following table describes for each parameter the collection time and the type of analyses to be done.

Parameter	Collection time	Main analyses (see section 5.2.3.8 describing the methodology)	Sensitivity analyses	Subgroup analyses
B-Crosslaps	Baseline, week 24	Descriptive analysis	None	By gender
Osteocalcin	Baseline, week 24	Descriptive analysis	None	By gender

### 5.3.3.3 Laboratory tests for safety assessment

The following parameters will be considered for the analyses:

- Haematology
  - o RBC count ( $10^{12}/L$ ),
  - o WBC count ( $10^9/L$ ),
  - o WBC differential: Neutrophil, Lymphocyte, Monocyte, Eosinophil, Basophil ( $10^9/L$ ),
  - o Reticulocytes ( $10^9/L$ ),
  - o Haemoglobin (g/L),
  - o Haematocrit (L/L),
  - o Platelet count ( $10^9/L$ ),
  - o Erythrocytes Mean Corpuscular Volume (MCV) (fL),
  - o Mean Corpuscular Haemoglobin Concentration (MCHC) (g/L)
- Chemistry
  - o Creatinine ( $\mu\text{mol}/L$ ),
  - o Urea (mmol urea/L),
  - o Albumin (g/L),
  - o Creatine PhosphoKinase (UI/L),
  - o eGFR ( $\text{mL}/\text{min}/1.73\text{m}^2$ )
- Liver/coagulation
  - o INR

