**Figure 1: NATIVE Study Design and Screening process**

**Table 1: Study Schedule of procedures (if a liver biopsy of less than 6 months is available before screening)**

Study Period	Screening	Treatment				Follow up
		V0	V1	V2	V3	
Visit	V-1	V0	V1	V2	V3	V4
Weeks (target+/-3days, referred to V0)	-4 to -2	0	4	14	24	28
Informed consent	X					
Inclusion/exclusion criteria	X	X				
Demographics, Medical history	X					
Alcohol consumption	X	X	X	X	X	X
Physical examination/ vital signs: height (inclusion only), weight, waist circumference, SBP, DBP, HR	X	X	X	X	X	X
12-lead Electrocardiogram	X		X		X	
Pregnancy test ((a): Blood test, $\beta$ HCG; (b): Urine Test)	X(a)	X(b)				
HIV serology	X					
Concomitant medications	X	X	X	X	X	X
Quality of life questionnaires		X			X	
Urine Samples		X		X	X	X
Blood Samples	X	X	X	X	X	X
FibroScan™ (if available)	X				X	
Central Reading of liver biopsy to confirm NASH diagnosis	X					
Liver biopsy at end of treatment					X	
Primary efficacy evaluation: Inflammation and ballooning SAF	X(c)				X	
Secondary efficacy evaluation						
NAS score and other liver histology indices	X				X	
Inflammatory markers fibrinogen, hs-CRP, alpha2-macroglobulin, haptoglobin levels		X			X	
Glucose metabolism fasting glucose and in subjects with T2DM: HbA1c	X	X	X	X	X	X
		X			X	
Lipids Lipids: TC, HDL-C, calculated LDL-C and TG	X	X	X	X	X	X
		X			X	
Chemistry Plasma Iron, Transferrin, Ferritin	X				X	
Fibrosis markers TIMP-1, TIMP-2, Cytokeratin K18, hyaluronic acid, P3NP, FGF 21		X			X	
Exploratory criteria Biobank						
Other biomarkers IL-6, IL-13, IL-17A, IL1B, TNF-<math>\alpha</math>, INF<math>\gamma</math>, APO B, APO C3, MMP2, MMP9, ProC3 (non-exhaustive list)		X			X	
Genotype PNPLA3, TM6FS2		X(d)				
Safety assessments						
Hematology WBC (+diff. Count), RBC, hemoglobin, MCV, hematocrit, Platelets, reticulocytes, CCMH, Hematocrit	X	X	X	X	X	X
Inflammatory markers Nt-ProBNP		X			X	
Chemistry creatinine, urea, albumin, CPK	X	X	X	X	X	X
Liver tests AST, ALT, ALP, GGT, total bilirubin	X	X	X	X	X	X
Bone B-Crosslaps, Osteocalcin		X			X	
Coagulation factors INR	X	X	X	X	X	X
Urine dipstick Hematuria		X		X	X	X
Pharmacokinetics: IVA337 (+ metabolites) trough sampling			X		X	
Adverse events		X	X	X	X	X

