**Table 8 : Central Laboratory tests for efficacy assessment**

Domain	Goal	Test	Screen	V0	V1	V2	V3	V4
	Efficacy	TIMP-1	-	✓	-	-	✓	-
	Efficacy	TIMP-2	-	✓	-	-	✓	-
	Efficacy	cytokeratin K18	-	✓	-	-	✓	-
	Efficacy	hyaluronic acid	-	✓	-	-	✓	-
	Efficacy	P3NP	-	✓	-	-	✓	-
Fibrosis	Efficacy	FGF 21	-	✓	-	-	✓	-
	Efficacy	Insulin	-	✓	-	-	✓	-
	Efficacy	Fasting glucose	✓	✓	✓	✓	✓	✓
	Efficacy	HbA1c	✓	✓	✓	✓	✓	✓
	Efficacy	peptide C	-	✓	-	-	✓	-
	Glucids	Efficacy	fructosamine	-	✓	-	-	✓
	Efficacy	Plasma Iron	✓	-	-	-	✓	-
	Efficacy	Transferrin	✓	-	-	-	✓	-
	Chemistry	Efficacy	Ferritin	✓	-	-	✓	-
	Efficacy	Fibrinogen	-	✓	-	-	✓	-
	Efficacy	hs-CRP	-	✓	-	-	✓	-
	Efficacy	Alpha2-macrogulin	-	✓	-	-	✓	-
	Inflammation	Efficacy	Haptoglobin	-	✓	-	-	✓
	Efficacy	Triglycerides	✓	✓	✓	✓	✓	✓
	Efficacy	HDL-C	✓	✓	✓	✓	✓	✓
	Efficacy	LDL-C	✓	✓	✓	✓	✓	✓
	Efficacy	Total-C	✓	✓	✓	✓	✓	✓
	Efficacy	FFA	-	✓	-	-	✓	-
	Efficacy	APO A1	-	✓	-	-	✓	-
	Efficacy	Adiponectin	-	✓	-	-	✓	-
Lipids	Efficacy	Leptin	-	✓	-	-	✓	-
	Efficacy	ALT	✓	✓	✓	✓	✓	✓
	Efficacy	AST	✓	✓	✓	✓	✓	✓
	Efficacy	AlcPhos	✓	✓	✓	✓	✓	✓
	Efficacy	Bilirubin total	✓	✓	✓	✓	✓	✓
	Liver	Efficacy	GGT	✓	✓	✓	✓	✓

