## **10. Patient Withdrawal & Replacement**

### **10.1 Patient Withdrawal**

Participation in the study is strictly voluntary. The patients have the right to withdraw from the study at any time for any reason, without the need to justify. The Investigator also has the right to withdraw patients in case of safety concerns, protocol deviations or administrative reasons. Since an excessive rate of withdrawals can render the study uninterpretable, the unnecessary withdrawal of patients must be avoided.

Reasons of withdrawal include, but are not limited, to the following:

- Patient decision
- Lost to follow-up, death

- Any AE, laboratory abnormality or illness which, in the opinion of the Investigator, indicates that continued treatment with study therapy and participation in the trial is not in the best interest of the subject.
- Major protocol deviation: e.g. lack of compliance with scheduled visits, non-compliance with study treatment, treatment with prohibited medication during the study (see 22)
- Any deterioration in cardiac status
- ALT or AST > 8 x ULN; or if ALT or AST > 5xULN for more than 2 weeks; or if ALT or AST > 3xULN and bili (total) > 2xULN (or INR>1.5); or ALT or AST > 3xULN and symptoms (Right Upper Quadrant pain, nausea, ...)
- Investigator's decision for any other reason

If a patient discontinues the study, the Investigator will make reasonable efforts to obtain the reason and to perform all protocol-defined end of study assessments as soon as possible. The reason and circumstances for premature discontinuation (e.g. consent withdrawal, AE, lost to follow up, etc.), and the date of withdrawal must be documented in the eCRF. If a patient discontinues the study for safety reasons, the outcome must be known.

In the case of withdrawal due to pregnancy (see paragraph 6.2.1), the patient will be followed until outcome, i.e. at least on a quarterly basis for follow-up evaluation of the pregnancy, foetus, delivery and new born. In the case of withdrawal due to an AE the patient will be followed until resolution of the AE, or until in the opinion of the Investigator the event has stabilized, and the patient is referred to their primary physician for appropriate management of the ongoing event. Reasonable efforts will be made to contact a patient who fails to attend any follow-up appointments, in order to ensure that he/she is in satisfactory health.

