## 4.5 Derived variables

### 4.5.1 Baseline data and change from baseline

Baseline data will be considered as the last available non-missing data before or equal to the treatment start.

*Note: For biopsies, multiple reading rules (see section 4.5.4.1.1) should be applied before calculating Baseline values.*

Absolute change from baseline will be calculated as follows:

Value at  $V_i$  – Value at baseline, where  $i$  corresponds to a post-baseline value.

Relative change from baseline (in %) will be calculated as follows:

- if Value at baseline is not equal to 0:  $[(\text{Value at } V_i - \text{Value baseline}) / \text{Value at baseline}] * 100$ , where  $i$  corresponds to a post-baseline value.
- if both values at  $V_i$  and at baseline are equal to 0, then the relative change from baseline will be equal to 0%.

Regarding laboratory parameters that are sensitive to the fasting status (Fasting Glucose, HOMA, insulin, C-peptid, Fructosamine, Triglycerides, Total cholesterol, HDL cholesterol, LDL cholesterol, Free fatty acids (FFA), Apoprotein A1, Apoprotein B, Apoprotein C3, Adiponectin, Leptin, FGF-21):

- if the value at Baseline is a non-fasting value when the value at Screening is a fasting value, then the Baseline data will be the value at Screening
- if both values at Screening and Baseline are non-fasting values, then the Baseline data will be the value at Baseline.

Regarding laboratory parameters, the following status will be defined:

- Normal-Normal, if the baseline is within laboratory ranges and all values over time remain within laboratory ranges
- Normal-Abnormal, if the baseline is within laboratory ranges but at least one value over time is not within laboratory ranges
- Abnormal-Normal, if the baseline is not within laboratory ranges and all values over time are within laboratory ranges
- Abnormal-Abnormal, if the baseline is not within laboratory ranges and at least one value over time is not within laboratory ranges

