Objectives/Endpoints	Type of analysis	Method of analysis	Population and imputation method
Glucose metabolism (fasting glucose, insulin, HOMA index, C-peptid, HbA1c and fructosamide)	Main analysis	Descriptive Treatment effect: MMRM or ANCOVA Time course: MMRM when possible	FAS – Observed Cases under treatment (considering only fasting values, when specified)
	Subgroups analysis (diabetic status) (HbA1c at for HbA1c)	Descriptive	FAS – Observed Cases under treatment (considering only fasting values, when specified)
Liver enzymes (ALT, AST, GGT, Alkaline Phosphatase, Total Bilirubin)	Main analysis	Descriptive Treatment effect: MMRM Time course: MMRM	FAS – Observed Cases under treatment
	Subgroup analysis (diabetic status)	Descriptive	FAS – Observed Cases under treatment
Plasma lipids levels (TC, HDL-C, LDL-C, TG, apoA1, FFA, Adiponectin, Leptin, APO B, APO C3 and FGF21)	Main analysis	Descriptive Treatment effect: MMRM or ANCOVA when specified Time course: MMRM when possible	FAS – Observed Cases under treatment considering only fasting values
	Subgroup analysis ; - diabetic status - statins at Baseline	Descriptive	FAS – Observed Cases under treatment considering only fasting values
Efficacy inflammatory markers (fibrinogen, hs- CRP, alpha2 macroglobulin, haptoglobin, IL-13, IL-17a, , IL-6, IL-1b, TNF-a, INFg)	Main analysis	Descriptive Treatment effect: ANCOVA when specified	FAS – Observed Cases under treatment

Objectives/Endpoints	Type of analysis	Method of analysis	Population and imputation method
Efficacy fibrosis markers (TIMP-1, TIMP-2, Hyaluronic acid, P3NP, NFS, FIB-4 score, ELF score, MACK-3, FIBC3, ABC3D, Cytokeratin M30, Cytokeratin M65, Liver iron content, MMP2, MMP9, Pro-C3)	Main analysis	Descriptive Treatment effect: ANCOVA when specified	FAS – Observed Cases under treatment
	Exploratory analysis	Cross-tabulation with the CRN-F score (F0-F1, F2-F3) when specified	FAS – Observed Cases under treatment
Efficacy chemistry markers (Plasma Iron, Transferrin, Ferritin)	Main analysis	Descriptive	FAS – Observed Cases under treatment

Subgroups of interest are :

(1)

- Biopsy length ( $\leq 8$ ,  $>8$  mm)
- SAF-A at Baseline (A2-A3, A4)
- CRN-F at Baseline (F0-F1, F2-F3)
- NAS score at baseline ( $<6$ ,  $\geq 6$ )
- BMI at Baseline (Obese, Non-Obese)Metabolic syndrome at Baseline (Yes, No)
- Insulin-resistance status at Baseline (Yes, No)
- Sex (Male, Female)

(2)

- NAS score at baseline ( $<6$ ,  $\geq 6$ )

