#### - Descriptive analysis

Fasting glucose and HbA1c assessed at Screening, Baseline, Week 4, Week 14, Week 24 and Week 28, as well as insulin, C-peptid, fructosamide and HOMA index assessed at Week 0 and Week 24, will be described over time using descriptive statistics by treatment group and diabetic status, in terms of:

- Raw values
- Absolute change from baseline

The 95% CI of the mean will also be provided.

- Status over time (Normal-Normal, Normal-Abnormal, Abnormal-Normal, Abnormal-Abnormal)

The 2 timepoints prior to first intake will have to be analysed: screening and baseline.

One graph will also be provided describing the raw values (with 95% CI) by treatment group over time (including screening values)

The HOMA index will also be described qualitatively over time using descriptive statistics by treatment group and diabetic status (HOMA < 3, ≥ 3).

- Absolute changes in HbA1c value will be described qualitatively over time using descriptive statistics by treatment group and diabetic status:
  - o Decrease of HbA1c (Decrease of 1%, No change (Change within ]-1% ; 1%[]), Increase ≥ 1%).
  - o Decrease of HbA1c (Decrease ≥ 0.5%, No change (Change within ]-0.5% ; 0.5%[]), Increase ≥ 0.5%)
- Evaluation of treatment effect (each dose versus placebo)

For fasting glucose, HbA1c, insulin and HOMA index, in order to evaluate each treatment dose versus placebo at week 24, a MMRM will be performed as detailed in section 4.1.5.

In order to take into account multiplicity of tests, the ascending Hochberg procedure will be applied (see section 4.1.5 for details).

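### The SAP plans no count, by arm, of patients who meet the protocol's own ALT, AST, bilirubin and INR criteria

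*SAP*

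**What the plan says.** - **Schedules** (Tables 1 and 2 of both documents): the row "AST, ALT, ALP, GGT, total bilirubin" stands among the safety assessments, with samples from screening to follow-up.
- **Protocol 6.3.2:** the same five tests appear in Table 8, "Central Laboratory tests for efficacy assessment". Table 7, the safety table, has only INR under liver.
- **SAP 5.3.3.3:** after "The following parameters will be considered for the analyses" come haematology, creatinine, urea, albumin, CPK, eGFR and INR. None of the five liver tests is there.
- **SAP 5.2.1:** "Liver enzymes (ALT, AST, GGT, Alkaline Phosphatase, Total Bilirubin" is a secondary efficacy item, analysed in the FAS on observed cases under treatment.
- **SAP 5.2.3.9** refers to the methods of 5.2.3.8: raw values, absolute change and "Status over time (Normal-Normal, Normal-Abnormal, Abnormal-Normal, Abnormal-Abnormal". ALT, AST and GGT also get the mixed model; ALP and bilirubin are descriptive only.
- **SAP 4.5.1** defines the last status class as "Abnormal-Abnormal, if the baseline is not within laboratory ranges and at least one value over time is not within laboratory ranges".
- **Protocol 5.3.7:** a safety visit follows when ALT reaches twice its V0 value or five times the ULN.
- **Protocol 10.1:** reasons for withdrawal include "ALT or AST > 8 x ULN; or if ALT or AST > 5xULN for more than 2 weeks", the joint criterion "if ALT or AST > 3xULN and bili (total) > 2xULN (or INR>1.5", and ALT or AST above 3xULN with symptoms.

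**The concern.** Safety is half of the study objective (SAP 3.1). The protocol names liver values that call for an extra visit or are grounds for withdrawal, so a reader of the report will want to know how many patients in each arm reached them. The planned summaries answer another question: how the average moved, and whether values were in or out of range. If treatment lowers enzymes in most patients and raises them sharply in a few, the average can look good while those few are visible only in a maximum, a listing or an adverse-event term.

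The omission does not look deliberate. The SAP sets cut-offs for QTcF and heart rate (4.5.6.4), weight (5.3.3.4) and HbA1c (5.2.3.8), and its section on departures from the protocol (4.6) records no decision to leave out liver cut-offs.

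**Working it through.** The plan gives no figure on this point, so there is none to reproduce. The check sets the criteria against the displays, then shows by arithmetic what a mean and a count can each tell.

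**1. Criteria against displays in the SAP text**

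| Protocol criterion | Counted by arm? |
|---|---|
| ALT 2 x V0 value (5.3.7) | No |
| ALT 5xULN (5.3.7) | No |
| ALT or AST >8xULN (10.1) | No |
| ALT or AST >5xULN for more than 2 weeks (10.1) | No |
| ALT or AST >3xULN with bilirubin >2xULN or INR >1.5 (10.1) | No; no joint display |
| ALT or AST >3xULN with symptoms (10.1) | No; no link to AE data |

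**2. What the status classes can show.** Abnormal means outside the laboratory range, with no multiple of the ULN. Take two patients whose baseline is above range. One stays at 1.2xULN and the other reaches 9xULN; both are Abnormal-Abnormal. Patients can start above range because entry allows ALT up to 10xULN (Protocol 4.2.1).

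**3. Which values can drop out**
- Non-biopsy values more than 3 days after last intake are set to missing (SAP 4.1.6.3). Week 28 is described, but not for patients who stopped early.
- Early-termination Visit 3 values are left out of Week 24 descriptions (SAP 4.1.6.3). A patient withdrawn under 10.1 can leave the Week 24 summary this way.
- After first intake, the first non-missing value is kept when there is a retest (SAP 4.5.6.3), so a higher or confirming retest is not used.
- Unscheduled and repeat results are listed, not summarised (Protocol 9.7.3). The 15-day ALT recheck of 5.3.7 is such a visit. The two-week criterion largely depends on repeats of this kind, because scheduled on-treatment visits after Week 4 are 10 weeks apart (Weeks 14 and 24).

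**4. What a mean shows.** Arm size: 247 randomised (SAP 3.5) / 3 = 82.3, taken as 82. The rises and falls below are assumptions for illustration.
- Two patients rise by 400 U/L: 2 x 400 / 82 = 9.8 U/L on the arm mean.
- Three patients rise from 1.5 to 5xULN (+3.5 each) while the other 79 fall by d. Mean change = (3 x 3.5 - 79d) / 82:
  - d = 0.2: (10.5 - 15.8) / 82 = -0.06xULN
  - d = 0.3: (10.5 - 23.7) / 82 = -0.16xULN
  - d = 0.5: (10.5 - 39.5) / 82 = -0.35xULN
- Masking is not certain. With five such patients and d = 0.2, the mean change is (17.5 - 15.4) / 82 = +0.03xULN.

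**5. What a count would show** (exact two-sided 95% limits, 82 per arm)
- 0 of 82: upper limit 1 - 0.025^(1/82) = 4.4%.
- 3 of 82: 3.7% (0.8% to 10.3%).
- Chance of at least one case in an arm, 1 - (1 - p)^82: 56%, 81% and 99% for assumed true rates of 1%, 2% and 5%.

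**The case against.** Four stronger readings are tempting, and the documents do not support them.

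- *A reader might infer that the SAP moved liver tests out of safety.* It did not. Protocol Table 8 already labels all five as efficacy, ALT, AST and GGT are protocol secondary endpoints, and SAP 5.3.3.3 follows Protocol Table 7 with eGFR added. The mismatch is between the schedules and Table 8.
- *A reader might infer that the efficacy label causes the gap.* Tests in 5.3.3.3 get the same three summaries on the same on-treatment values, and the FAS and Safety set both require randomisation and at least one dose. Moving the tests there would produce no threshold count. What is missing is the cut-offs.
- *A reader might infer that liver injury would be invisible, or that the trial could say nothing on liver safety by arm.* SAP 4.1.4 reports minimum and maximum, so a large rise at a scheduled on-treatment visit shows as that arm's maximum. Clinically significant abnormalities become adverse events (Protocol 6.3, 9.7.3). TEAEs, including those leading to permanent discontinuation, are tabulated by arm (SAP 5.3.2), and reasons for stopping are described (SAP 5.1.1). The protocol promises shift tables for tests of interest, though it does not name them. The DSMB sees main laboratory results by coded arm.
- *A reader might infer that no table exists.* The shells are in an appended document that was not available, so the statement covers the SAP text only.

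This cover is real but partial. A maximum is neither a count nor a joint criterion, and the adverse-event route depends largely on investigator judgement and coding.

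One further objection stands and shapes the fix. Because entry allows ALT up to 10xULN, a raw count would mix baseline elevation with new rises. The entry limit and the 8xULN withdrawal criterion also overlap, and the sponsor must reconcile those passages; this review takes no position on which should govern.

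**Conclusion.** The point holds in a limited form. On the SAP text, no planned analysis gives the number of patients per arm meeting any ALT, AST, bilirubin or INR criterion of Protocol 5.3.7 or 10.1. The four status classes cannot stand in for it, and several data rules can drop the values that would show a crossing. It is a gap in how liver safety is displayed, not a failure to collect or assess it. Alpha, power and sample size are unaffected.

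The size cannot be fixed from the documents, which do not say how many patients start above range or how many might cross a criterion. The 400 U/L rises, the xULN changes and the true rates are assumptions; only the 247 randomised is a document figure, and 82 per arm assumes an even split. On that basis the table would support statements such as 0 of 82 with an upper limit of 4.4%, which the present text does not yield.

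**What to change.** Add to SAP 5.3.3 a Safety-set table, by arm, with these features:

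- The number and percentage of patients who newly meet, after first dose, each criterion of Protocol 5.3.7 and 10.1, including the joint ALT or AST with bilirubin or INR criterion.
- Patients already above a cut-off at baseline shown separately, or multiples of baseline given as well.
- All post-baseline values used: scheduled, unscheduled, retest, early-termination and follow-up. State that the on-treatment window and the first-value retest rule do not apply to this table.
- The symptom criterion linked to adverse-event data, or its laboratory part reported alone and labelled so.

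If the appended shells already contain such a table, the SAP text need only define it and refer to it.

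The cost is a small amount of programming on data already collected, somewhat more than a single standard table because of the baseline rule, the two-week duration and the adverse-event link. No other analysis changes.

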### **Main analysis**

The population of analysis will be the Safety Set as described in section 4.3.4. Only the observed cases under treatment will be analysed (see section 4.1.6.3).

- Descriptive analysis

Each parameter will be described at each study visit using descriptive statistics by treatment group in the safety set of patients, in terms of:

- Raw values
- Absolute change from Baseline
- Status over time (Normal-Normal, Normal-Abnormal, Abnormal-Normal, Abnormal-Abnormal)

Then, for each parameter, will be provided a graph reporting the mean (95% CI) of the parameter by visit and treatment group.

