#### 9.7.3 *Other Observations Related to Safety*

### - **Laboratory tests**

The analysis will include patients exposed to study medication who have at least one laboratory test performed after the first study product intake and, when required by the definition of the abnormality, with an available baseline value and available normal ranges. For these descriptions, the baseline value will be the latest available measure before the first study product dose intake. International units will be used in all listings, tables and graphs. Results and changes from baseline of laboratory parameters will be summarized by mean, standard deviation, median, minimum and maximum at each time point and for the final on-treatment visit. Unscheduled and/or repeated results will only be listed and not summarized.

Shift tables and other tabular and graphical methods will be used to present the results for tests of interest. Listings will be provided with flags indicating clinically significant out-of-range values, clinically non-significant out-of-range values.

In addition, out-of-range values will be assessed by the investigator as clinically significant or not clinically significant. Abnormal laboratory tests assessed by the investigator as clinically significant will be reported as an AE.

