###### All other procedures:

Only observed cases within 3 days after study treatment last intake will be used:

- Missing data will remain missing
- Will also be considered as missing any data collected more than 3 days after study treatment last intake

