###### Note:

- Data collected at Visit 3 being an early treatment discontinuation, should not be taken into account for Week 24 (i.e. actual V3) data descriptions
- For OCUT analysis where data available at Week 28 (i.e. V4) should be described, all Week 28 (i.e. V4) data that are within 4 weeks  $\pm$  2 weeks compared with Week 24 (i.e. V3) are to be taken into account.  
Data collected at Visit 4 being the visit following an early treatment discontinuation, should not be taken into account for Week 28 (i.e. actual V4) data descriptions
- For all analysis based on biopsy data, data collected at actual V3 should be taken into account as well as data collected at Visit 3 being an early treatment discontinuation.

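### Safety laboratory summaries, as worded, have no row for an early stopper's termination and follow-up values, and the protocol's final on-treatment summary is absent from the SAP text

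*SAP*

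**What the plan says.** SAP 5.3.3.3 describes 19 haematology, chemistry and coagulation parameters by study visit and arm in the Safety Set, and states that "Only the observed cases under treatment will be analysed (see section 4.1.6.3"). SAP 5.3.3.1 applies the same restriction to NT-proBNP and plans a listing of abnormal values at baseline and/or Week 24. The bone markers (5.3.3.2) and the liver tests (5.2.3.9) inherit the restriction by pointing to the method in 5.2.3.8.

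SAP 4.1.6.3 defines what counts as under treatment. For procedures other than biopsy: "Will also be considered as missing any data collected more than 3 days after study treatment last intake". Its closing note adds two exclusions: "Data collected at Visit 3 being an early treatment discontinuation, should not be taken into account for Week 24" and "Data collected at Visit 4 being the visit following an early treatment discontinuation, should not be taken into account for Week 28". For biopsy data the same note goes the other way: "data collected at actual V3 should be taken into account as well as data collected at Visit 3 being an early treatment discontinuation". It makes no such provision for laboratory data.

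Protocol 5.0 section 9.7.3 says that laboratory results and changes from baseline will be "summarized by mean, standard deviation, median, minimum and maximum at each time point and for the final on-treatment visit". The SAP text contains no final on-treatment summary, and SAP 4.6, which records departures from the protocol's statistical section, does not mention its removal.

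**The concern.** Whether a laboratory value reaches a by-visit safety table depends partly on whether the patient stopped treatment. Protocol 10.1 names laboratory abnormality among the reasons for stopping, so the values without a row are not a random subset. The protocol does ask for these samples: sections 5.3.4 and 5.3.5 request the Visit 3 assessments and the later follow-up visit from patients who withdraw, where feasible. Section 10.1 asks for the end-of-study assessments promptly but sets no 3-day limit. The data would therefore be collected and then have no stated place in the by-arm numeric summaries.

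The final on-treatment visit summary is the natural way to show each patient's last on-drug value whenever that patient stopped, and its absence makes the gap matter more. NT-proBNP is the sharpest case. Its only scheduled post-baseline sample is Visit 3 (Protocol Table 7), and its only planned output names baseline and Week 24.

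**Working it through.** The plan states no figure on this point, so the check applies its rules to each kind of sample.

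| Sample | 3-day window | Row in the by-visit tables | Other possible place |
|---|---|---|---|
| V1, V2 while on drug | inside | Week 4, Week 14 | status over time |
| Early-termination V3, 0 to 3 days after last intake | inside | barred from Week 24; no other row named | status over time, by general wording |
| Early-termination V3, 4 or more days after last intake | outside: missing | none | none in these tables |
| V4 following an early stop | outside | barred from Week 28; no other row named | none in these tables |
| Completer's V4 | covered by its own allowance | Week 28 | – |

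- Follow-up after an early stop: V4 is planned 4 weeks (28 days) after the end of treatment. With the termination visit 0, 2, 3, 4 or 10 days after last intake and V4 28 days later, V4 falls at 28, 30, 31, 32 or 38 days. All exceed 3.
- The completer's allowance ("For OCUT analysis where data available at Week 28 (i.e. V4) should be described") is 4 weeks plus or minus 2 weeks from Week 24, that is 2 to 6 weeks, or 14 to 42 days. It runs from an actual Week 24 visit, so it does not help an early stopper.

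**Outputs concerned**
- SAP 5.3.3.3: 13 haematology + 5 chemistry + INR = 19 parameters.
- SAP 5.2.3.9: ALT, AST, GGT, alkaline phosphatase and total bilirubin = 5. For these and the 19 above, V1 and V2 values remain.
- NT-proBNP, B-Crosslaps and osteocalcin = 3, each with Visit 3 as the only scheduled post-baseline sample. The two bone markers use the 5.2.3.8 method, which includes status over time, so a value within 3 days of last intake may still count there. NT-proBNP has only the listing.

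**Number of patients**
- SAP 3.5 gives 247 randomised, so 247 / 3 = 82.3 per arm.
- The documents give no early-stop rate. Assuming 5 to 15%: 247 × 0.05 = 12.4 and 247 × 0.15 = 37.1 overall; 82.3 × 0.05 = 4.1 and 82.3 × 0.15 = 12.3 per arm.
- These are upper limits for that range, since not every early stopper will attend Visit 3. They count patients, not abnormal results.

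**Protocol against SAP**
- Protocol 9.7.3 lists the final on-treatment visit in addition to each time point, so it promises something beyond the by-visit tables.
- SAP 4.6 covers terminology, populations, endpoints, efficacy analysis, subgroups and liver iron content. Laboratory summaries are not among them.

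**The case against.** The strongest reply is that the plan already covers this. SAP 5.1.1 splits Visits 3 and 4 for analysis into early-termination and on-schedule visits and gives the CRF design as the reason, which applies study-wide. Barring a value from the Week 24 row is not the same as discarding it, and the row layout is left to appended mock-ups that were not available. This may be the intention. But the split sits under patient disposition, and no laboratory section takes it up.

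A second reply is that the SAP follows protocol 5.1, whereas only 5.0 was available, and that the protocol lets SAP clarifications prevail. The version point stands, so the omission can be asserted only for the SAP text against 5.0. An unrecorded omission is not a clarification, however.

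A third reply concerns harm. A reader might infer that early stoppers' laboratory data disappear from the safety reporting, or that a signal would be hidden. The documents do not support that:
- Results judged clinically significant are reported as adverse events (Protocol 9.7.3). They enter the treatment-emergent tables up to 28 days after last dose, including the table of events leading to permanent discontinuation (SAP 4.5.6.2 and 5.3.2.2).
- Protocol 9.7.3 calls for listings that flag out-of-range values, whether or not clinically significant.
- SAP 4.5.1 defines status over time by any value over time, so termination values within 3 days of last intake may count, including for the bone markers.
- An abnormality serious enough to prompt a stop would ordinarily be judged clinically significant.

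Nor is the contrast with completers fully like for like. Their Week 28 value is the planned follow-up, and the 3-day rule also removes a completer's late Visit 3. No distortion between arms has been shown.

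**Conclusion.** The point holds in a limited form. As worded, the SAP gives an early stopper's termination and follow-up laboratory values no row in the by-visit summaries, and it leaves a termination NT-proBNP value outside the listing. It also lacks a summary that protocol 5.0 promises, without recording the change. What can go unsummarised by arm is the numeric values, and abnormalities not judged clinically significant, at or after an early stop.

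The size is at most about 4 to 12 patients per arm if 5 to 15% stop early, and that rate is an assumption. The conclusion rests on the SAP text and protocol 5.0. If protocol 5.1 dropped the final on-treatment summary, or the mock-ups already carry an early-termination row, a sentence in the SAP would close that part. It should be settled because the affected patients may have stopped for a laboratory reason and the repair is cheap.

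**What to change.** 1. Keep the by-visit tables restricted to observed cases under treatment.
2. Add the final on-treatment visit summary by arm for the 5.3.3.3 parameters, and for ALT, AST and total bilirubin, on the Safety Set. If protocol 5.1 removed this summary, record that in SAP 4.6.
3. Carry the 5.1.1 split into the laboratory and bone tables: show early-termination Visit 3 as a separate row, with days since last intake flagged.
4. Include early-termination Visit 3 values in the NT-proBNP listing, with the same flag.
5. State in SAP 4.5.1 that early-termination values count in status over time.

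These changes use scheduled or withdrawal-visit samples, so they leave intact the protocol's rule that "Unscheduled and/or repeated results will only be listed and not summarized". The cost is SAP wording and a few extra tables, with no new data. The drawback is that the early-termination row will hold few patients at mixed times, so it should be read descriptively.
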